

[10] van der Maas NG, von Asmuth EGJ, Berghuis D, et al. Modeling influencing factors in B-cell reconstitution after hematopoietic stem cell transplantation in children. *Front Immunol*. 2021;12:684147.

2. Study objective

To assess the effectiveness of interventions including health monitoring and regular return follow-up reminders for patients with a high CIRS.

3. Study design

This is a prospective multi-center randomized-controlled clinical trial.

4. Study population

Adult patients receiving allo-HSCT.

4.1 Inclusion criteria

- 1) Patients must be ≥ 16 years of age;
- 2) Patients receiving haploidentical allo-HSCT;
- 3) Patients have to sign an informed consent form before the start of the research procedure.

4.2 Exclusion criteria

Patients who meet any of the following criteria will not be enrolled in the study:

- 1) Tandem transplantation or multiple transplantations;
- 2) Mental or other medical conditions that make the patients unable to comply with the research treatment and monitoring requirements;
- 3) Patients who are ineligible for the study due to other factors, or will bear great risk if participating in the study.

4.3 Drop-out and withdrawal criteria

A patient may withdraw from the study if he/she does not wish to continue participating in the study, and the date and reason for withdrawal shall be recorded.

The investigator may also decide to discontinue a patient from the clinical study if there is an unacceptable risk.

5. Study regimen

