5.1 Risk prediction

The patients were randomly divided into intervention group and control group (the probability of entering the intervention group is 0.5). Physicians assessed the risk level of patients in the intervention group based on their immune status on days 91-180 using the CIRS.

- Scored as high risk: health monitoring & reminders for blood tests weekly & reminders for follow-up visits until 1 year post-transplant.
- Scored as intermediate risk: health monitoring & reminders for blood tests monthly & reminders for follow-up visits until 1 year post-transplant.
- Scored as low risk: reminders for follow-up visits until 1 year post-transplant.

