5.3 Early warning and suggestion

When there is any abnormality in the patient's daily health monitoring information, the app will suggest the patient to consult the doctor in time or send a message to remind the doctor to pay attention to the patient's condition.

[figure not shown]

Figure 1. Study flowchart

6. Study assessment and follow-up

Patients will be regularly followed up after transplantation. Data on infection, relapse and survival will be collected.

7. Study endpoints

- Primary endpoint: survival after transplantation.
- Secondary endpoints: non-relapse mortality rate, relapse rate, incidence of infections and immune cells count.

8. Sample size calculation

456 transplant patients are expected to be enrolled.

The 1.5-year survival rates of previous adult patients at the IHCAMS was 86% during 1 January 2019 – 31 December 2021. The 1.5-year survival rates of intervention group will improve to 92% per the researchers' estimation. To attain a 0.05 significance level and a 0.8 power at a presumed 10% dropout rate, ≥ 456 participants will need to be enrolled.

9. Statistical analysis

SAS and R statistical analysis software will be used to conduct the statistical analysis tailored to data properties. All comparison tests will be two-sided, and statistical significance will be defined as $P < 0.05$ in all the analyses.

10. Ethical review

The study will be conducted in accordance with the Declaration of Helsinki (2013), relevant regulations issued by the government of the People's Republic of China, and additional precautions required by the ethics review committee at the IHCAMS.

Before the study, the investigator will obtain approvals from the ethics review committee at the IHCAMS regarding the study protocol data sheet, informed consent form, subject enrollment form, and other relevant information to be provided to the subject before enrollment. During the study, if there is any amendment to the study protocol data sheet, informed consent form, subject enrollment form, and other relevant information to be provided to the subject before enrollment, renewed approvals shall be obtained from the IHCAMS ethics review committee before continuation of the study.

11. Preservation of research data

All data of this study will be stored at the IHCAMS. Data sharing among the researchers will abide by the regulations of the People's Republic of China regarding desensitization.

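### Does the investigator's right in section 4.3 to discontinue a patient for risk cut off survival follow-up and bias the primary endpoint?

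*Protocol*

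**What the plan says.** Section 4.3 has two sentences. The first lets a patient withdraw and adds that "the date and reason for withdrawal shall be recorded". The second gives the investigator a parallel right: "The investigator may also decide to discontinue a patient from the clinical study if there is an unacceptable risk". Neither says what happens to outcome collection afterwards.

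Section 6 is equally short: "Patients will be regularly followed up after transplantation", and "Data on infection, relapse and survival will be collected". It sets no condition about still being on study procedures and makes no exception for discontinued patients.

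Three other places bear on the point:

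- Section 7 names the endpoint: "Primary endpoint: survival after transplantation".
- Section 8 plans on survival at 1.5 years, 86% against 92%, with the sample size set "at a presumed 10% dropout rate". It does not say where those dropouts come from.
- Section 5.1 runs the reminders to 1 year after transplant, and describes risk scoring for one arm only: "Physicians assessed the risk level of patients in the intervention group based on their immune status on days 91-180 using the CIRS".

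**The concern.** Three features together look worrying.

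- **Scope of removal.** Section 4.3 speaks of leaving the study, not of stopping the app or the reminders. Under a heading about drop-out and withdrawal, a site could take it that data collection stops too.
- **Ground for removal.** The ground is risk and the endpoint is death. Patients removed for risk could have a worse prognosis than those who stay, so their loss would be informative.
- **Knowledge of the arm.** The trial appears unblinded, and the CIRS is scored only in the intervention group, so removals could differ between arms.

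If all three applied, the survival comparison would be biased, and no analysis could recover deaths that were never collected. A SAP can decide how to treat missing outcomes but cannot make sites collect them, so the absence of the SAP here would not answer the point. The duty to record date and reason also stands only in the sentence on patient withdrawal.

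**Working it through.** **1. The passages side by side.** The concern needs section 4.3 read broadly (removal ends everything) and section 6 read narrowly (follow-up covers only patients still on procedures). Section 6 does not carry the narrow reading: its subject is patients and its anchor is transplantation. No sentence states that follow-up ends at discontinuation.

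**2. The time horizons.** Reminders end at 1 year (section 5.1). Survival is planned at 1.5 years (section 8). For at least 1.5 − 1 = 0.5 years, survival must be collected from patients on whom no study procedure is running. The design therefore already separates the end of procedures from the end of survival follow-up.

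**3. The route to removal.** The intervention is self-recorded health data, app alerts and reminders. Section 4.2, third criterion, already keeps out patients for whom taking part would carry great risk. A high CIRS leads to closer monitoring in section 5.1, and no passage links it to removal. No control-arm procedure is described that would give a reason for removal on risk grounds.

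**4. Size if patients were lost all the same.** The protocol gives no figure for such losses, so there is none to reproduce.

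Inputs from section 8 and section 5.1: 456 patients allocated 1:1, so 456/2 = 228 per arm; mortality m = 1 − 0.86 = 0.14; planned difference 92 − 86 = 6 points. The 456 is taken as given, and the point does not depend on whether it is adequate.

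Assumptions: a share f = 2% or 5% of one arm is lost (228 × 0.02 = 4.6 or 228 × 0.05 = 11.4 patients), with mortality r times the arm's average, r = 1 to 4, and no true treatment effect.

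*(a) Lost patients dropped altogether.* Apparent mortality = m(1 − f·r)/(1 − f). For f = 0.05 and r = 4: 0.14 × (1 − 0.20)/0.95 = 0.1179, a shift of 14.00 − 11.79 = 2.21 points. Rejection rates are for a two-sided 5% pooled z test with 228(1 − f) against 228 patients.

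*(b) Time at risk kept.* Kaplan-Meier estimate at 1.5 years, exponential deaths, discontinuation uniform over 0 to 1.5 years. Standard error of the difference = √(2 × 0.14 × 0.86/228) = 0.0325, or 3.25 points. Rejection rate = Φ(−1.96 + shift/SE) + Φ(−1.96 − shift/SE). For f = 0.05 and r = 4, shift/SE = 0.96/3.25 = 0.295, and Φ(−1.665) + Φ(−2.255) = 0.048 + 0.012 = 0.060.

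| f | r | (a) shift, points | (a) rejection | (b) shift, points | (b) rejection |
|---|---|---|---|---|---|
| 2% | 1 | 0 | 5.0% | 0 | 5.0% |
| 2% | 2 | 0.29 | 5.1% | 0.14 | 5.0% |
| 2% | 3 | 0.57 | 5.4% | 0.26 | 5.1% |
| 2% | 4 | 0.86 | 5.8% | 0.38 | 5.2% |
| 5% | 1 | 0 | 5.0% | 0 | 5.0% |
| 5% | 2 | 0.74 | 5.6% | 0.35 | 5.1% |
| 5% | 3 | 1.47 | 7.4% | 0.68 | 5.5% |
| 5% | 4 | 2.21 | 10.6% | 0.96 | 6.0% |

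*(c) A true difference of 14% against 8% mortality, lost patients dropped as in (a).* Equal losses in both arms at r = 2 to 4 leave 5.88 to 5.63 of the 6 points (2% lost) or 5.68 to 5.05 (5% lost). Losses in the control arm only leave 5.71 to 5.14 or 5.26 to 3.79.

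The large figures need several things at once: about 11 patients removed for risk from one arm and none from the other, mortality among them of 4 × 14% = 56%, and an analysis that discards the time they were observed. For a survival endpoint that time is normally kept, and column (b) then applies.

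**The case for a change.** The best case for the concern is that follow-up after discontinuation belongs in a protocol, because sites act on the protocol. Section 6 neither names discontinued patients nor gives an end date. Section 8 allows for 10% dropout, so the authors do expect some loss. The sentence needed would be cheap, and missing deaths cannot be regained later. Without a recorded reason for each removal, the trial could not show afterwards whether removals were few, balanced or unrelated to prognosis.

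Part of this stands. Section 4.3 would be clearer if it addressed follow-up after discontinuation, and the unseen SAP does not settle what sites collect. The rest is weaker. The 10% is not attributed to investigator removals and may simply reflect patients who withdraw or lose contact. The two sentences of section 4.3 stand under one heading, and the second is joined to the first by 'also'. To read the recording duty as deliberately leaving out investigator decisions is strained, and such items are usually fixed in the case report form, which is not at hand. That a change is cheap does not make its absence a defect.

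**Conclusion.** No finding. The protocol contains no statement that survival follow-up stops at discontinuation. Section 6, read in its ordinary sense, covers these patients, and the 1.5-year horizon already requires follow-up beyond the 1-year procedures. What remains is a missing clarification, not something stated wrongly, contradicted or badly fixed.

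The possible harm rests wholly on assumed loss rates and mortality ratios. It is zero if lost patients have average mortality. With time at risk kept, the worst assumed case (5% of one arm lost at four times average mortality) moves apparent survival by just under 1 point and raises the rejection rate from 5% to about 6%. The 10.6% figure arises only if those patients' observed time is also thrown away. The actual number of such removals in an app-and-reminder trial may be near zero. The judgement would change if other trial documents told sites to stop collecting vital status at discontinuation; nothing in the protocol does.

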5.1 Risk prediction

The patients were randomly divided into intervention group and control group (the probability of entering the intervention group is 0.5). Physicians assessed the risk level of patients in the intervention group based on their immune status on days 91-180 using the CIRS.

- Scored as high risk: health monitoring & reminders for blood tests weekly & reminders for follow-up visits until 1 year post-transplant.
- Scored as intermediate risk: health monitoring & reminders for blood tests monthly & reminders for follow-up visits until 1 year post-transplant.
- Scored as low risk: reminders for follow-up visits until 1 year post-transplant.

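### The objective is worded for high-CIRS patients, but as described the trial compares whole arms and gives controls no CIRS category

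*Protocol*

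**What the plan says.** - **Objective (Section 2):** "To assess the effectiveness of interventions including health monitoring and regular return follow-up reminders for patients with a high CIRS". This is the only objective stated.
- **Entry (Sections 4.1 and 4.2):** the criteria cover age, transplant type ("Patients receiving haploidentical allo-HSCT"), consent and general exclusions. None refers to CIRS.
- **Allocation (Section 5.1):** "The patients were randomly divided into intervention group and control group (the probability of entering the intervention group is 0.5"). This covers all patients, with no restriction to a risk tier.
- **Scoring (Section 5.1):** "Physicians assessed the risk level of patients in the intervention group based on their immune status on days 91-180 using the CIRS". No section describes scoring of controls.
- **Intervention (Section 5.1):** high- and intermediate-risk patients receive monitoring and reminders at different frequencies. The lowest tier is also treated: "Scored as low risk: reminders for follow-up visits until 1 year post-transplant".
- **Data (Section 6):** "Data on infection, relapse and survival will be collected". Immune counts are not in this list.
- **Endpoints (Section 7):** "Primary endpoint: survival after transplantation", with no CIRS restriction. The secondary endpoints are "non-relapse mortality rate, relapse rate, incidence of infections and immune cells count".
- **Sample size (Section 8):** 456 patients, from 1.5-year survival of 86% in the centre's earlier adult patients against 92% expected in the intervention group.
- **Background (before Section 2):** the score combines eight immune factors, and the day 91–180 score was an independent risk factor for early mortality (hazard ratio 1.80, 95% CI 1.28 to 2.55).

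**The concern.** Read plainly, Section 2 asks whether monitoring and reminders help patients with a high CIRS. Answering that from randomised data needs high-CIRS patients in both arms, identified in the same way. The protocol describes them in one arm only.

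The whole-arm result averages over three tiers that receive three different interventions. A positive result would not show that high-CIRS patients benefited, and a null result would not show that they did not. There is also a risk that someone later sets the scored high-CIRS patients of the intervention arm against all controls. That contrast is not randomised, because one side is selected for poor prognosis and the other is not.

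Timing matters too. The score uses immune status in a fixed window after transplant. If controls have no usable counts from that window, no later analysis plan can create them.

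**Working it through.** The point is one of consistency, so the main check sets the sections side by side.

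**1. Population by section**

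| Section | Population |
|---|---|
| 2 Objective | High CIRS, as worded |
| 4 Entry | All eligible patients, any CIRS |
| 5.1 Allocation | All patients, probability 0.5 |
| 5.1 Scoring | Intervention arm only |
| 5.1 Intervention | All three tiers |
| 7 Primary endpoint | No CIRS restriction |
| 8 Sample size | Whole arms, 86% vs 92% |

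Only Section 2 singles out high CIRS.

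**2. The plan's own figure.** Inputs from Sections 8 and 9 are 0.86 vs 0.92, two-sided 0.05, power 0.80 and 10% dropout. Two-proportion formula with pooled variance, per arm:

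n = [1.96·√(2·0.89·0.11) + 0.8416·√(0.86·0.14 + 0.92·0.08)]² / 0.06² = 426

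The total is 852, and 852/0.9 = 947 after dropout. The stated total of 456 is therefore not reproduced by this formula. That is a separate matter on which this point does not rest. What matters here is that both survival inputs are whole-arm rates, so 456 was not derived for a high-CIRS comparison by any method.

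**3. Why unscored controls cannot stand in.** The hazard ratio implied by the planned effect is ln(0.92)/ln(0.86) = 0.553, and its inverse is 1/0.553 = 1.81. The reported prognostic hazard ratio of the score is 1.80. Setting high-CIRS intervention patients against all controls therefore brings in a prognostic difference that could approach the planned effect and run the opposite way. This indicates order of magnitude only. The contrast behind 1.80 is not stated, it was reported for early mortality, and the control arm itself contains some high-CIRS patients, which narrows the gap.

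**4. Could controls be scored later?** Immune cell counts are a secondary endpoint, which suggests that some are taken. The protocol does not say in which arm, in which window, or whether all eight factors are covered. Section 6 omits them from its data list. Figure 1 is not shown. The document leaves the question open.

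**5. Why no power figure is given.** The high-CIRS share, the contrast behind 1.80 and the timing of deaths are not given. Even the post-scoring treatment effect is not fixed. It is 0.553 if no deaths precede scoring. If, as an assumption, 4% of each arm died before scoring, reaching 92% overall would need ln(0.92/0.96)/ln(0.86/0.96) = 0.387. Any power figure would mainly reflect such assumptions.

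**The case against.** The strongest reply is that Section 2 need not define an analysis population. Its closing phrase can attach to the reminders or the interventions, so that the sentence describes what the strategy delivers. Sections 4, 5.1, 7 and 8 all fit a trial of a CIRS-guided strategy against control, and in such a trial the score is part of the intervention. Scoring one arm for care is then no error. This reading is reasonable, and it cannot be ruled out. It does not make the text consistent, because Section 2 would then name one of the three tiers that Section 5.1 treats.

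A second reply is that subgroup analyses belong in the statistical analysis plan, which is not shown. That holds for defining the analysis. It does not hold for which patients have counts taken in days 91–180.

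Three stronger readings are tempting and are not supported:

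- *A reader might infer that the randomised comparison is invalid.* It is not. Whole arm against whole arm is a sound test of the strategy.
- *A reader might infer that control scores will not exist and the gap is beyond repair.* The document does not say so. Section 5.1 does not forbid calculating the score in controls, and the secondary endpoint may supply the counts.
- *A reader might infer that a high-CIRS comparison would have hopelessly low power.* The inputs needed to say so are not given, and the answer changes materially with the assumed timing of deaths and with how far the benefit concentrates in one tier.

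**Conclusion.** The inconsistency is real and worth correcting. As described, the trial can estimate the effect of a CIRS-guided strategy in all patients, but not an effect specific to those with a high CIRS. This rests on the wording of Sections 2, 4, 5.1, 7 and 8, and on the score being prognostic, as the background reports. It does not rest on any power calculation.

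The consequence is limited to what may be concluded; allocation and the primary comparison stand. Confidence is medium, because Section 2 admits two readings and the availability of control counts is not stated. If the strategy reading is intended, what remains is a one-sentence wording fault.

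**What to change.** Reconcile Sections 2, 5.1, 6 and 8 by one of two routes.

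1. **Keep the high-CIRS objective.** State in Section 5.1 that CIRS is calculated in both arms by the same rule from day 91–180 counts. In controls the score would be for analysis only, using counts already collected where possible. Add those counts to the data list in Section 6. Describe the between-arm comparison in high-CIRS patients as an estimate that N = 456 was not sized to test. *Cost:* protocol wording, and possibly an extra panel in some controls. The choice should be made before the day 91–180 window closes for enrolled patients.
2. **Make the strategy the objective.** Reword Section 2 to a CIRS-guided strategy in all enrolled patients, and draw no conclusion specific to high CIRS. *Cost:* one sentence and a narrower conclusion.

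Neither route changes the randomisation or the whole-arm primary comparison.

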5.2 Health surveillance

Things as follows will be recorded by patients every day using the app:

- 1) Body temperature
- 2) Body weight
- 3) White blood cell count, platelet, hemoglobin
- 4) Total bilirubin, alanine aminotransferase, glutamine aminotransferase, creatinine
- 5) Any discomfort? (Difficulty in breathing, cough, sputum, abdominal pain, diarrhea, vomiting, palpitations, chest pain, Frequent, urgent or painful urination, edema of eyelids or lower extremities, dry eyes or mouth, new rash, bleeding from nose or gums or visible bleeding spots on skin, drowsiness or impaired consciousness)

5.3 Early warning and suggestion

When there is any abnormality in the patient's daily health monitoring information, the app will suggest the patient to consult the doctor in time or send a message to remind the doctor to pay attention to the patient's condition.

[figure not shown]

Figure 1. Study flowchart

6. Study assessment and follow-up

Patients will be regularly followed up after transplantation. Data on infection, relapse and survival will be collected.

7. Study endpoints

- Primary endpoint: survival after transplantation.
- Secondary endpoints: non-relapse mortality rate, relapse rate, incidence of infections and immune cells count.

8. Sample size calculation

456 transplant patients are expected to be enrolled.

The 1.5-year survival rates of previous adult patients at the IHCAMS was 86% during 1 January 2019 – 31 December 2021. The 1.5-year survival rates of intervention group will improve to 92% per the researchers' estimation. To attain a 0.05 significance level and a 0.8 power at a presumed 10% dropout rate, ≥ 456 participants will need to be enrolled.

9. Statistical analysis

SAS and R statistical analysis software will be used to conduct the statistical analysis tailored to data properties. All comparison tests will be two-sided, and statistical significance will be defined as $P < 0.05$ in all the analyses.

10. Ethical review

The study will be conducted in accordance with the Declaration of Helsinki (2013), relevant regulations issued by the government of the People's Republic of China, and additional precautions required by the ethics review committee at the IHCAMS.

Before the study, the investigator will obtain approvals from the ethics review committee at the IHCAMS regarding the study protocol data sheet, informed consent form, subject enrollment form, and other relevant information to be provided to the subject before enrollment. During the study, if there is any amendment to the study protocol data sheet, informed consent form, subject enrollment form, and other relevant information to be provided to the subject before enrollment, renewed approvals shall be obtained from the IHCAMS ethics review committee before continuation of the study.

11. Preservation of research data

All data of this study will be stored at the IHCAMS. Data sharing among the researchers will abide by the regulations of the People's Republic of China regarding desensitization.

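### 456 patients in total give about 50% power for 86% versus 92% survival at 1.5 years, not the stated 80%; the figure appears to be a per-arm number

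*Protocol*

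**What the plan says.** Section 8 (Sample size calculation) gives the enrolment target twice, both times for the whole trial: "456 transplant patients are expected to be enrolled", and then "To attain a 0.05 significance level and a 0.8 power at a presumed 10% dropout rate, ≥ 456 participants will need to be enrolled". Nothing there or elsewhere in the protocol says that 456 is a number per group.

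The effect assumed is in the same section. For controls: "The 1.5-year survival rates of previous adult patients at the IHCAMS was 86% during 1 January 2019 – 31 December 2021". For the intervention: "The 1.5-year survival rates of intervention group will improve to 92% per the researchers' estimation".

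Two further inputs come from other sections. Section 5.1 sets equal allocation ("the probability of entering the intervention group is 0.5"), and Section 9 fixes the sidedness ("All comparison tests will be two-sided"). The primary endpoint in Section 7 is survival after transplantation. The protocol does not name the formula behind 456.

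**The concern.** A difference of 6 percentage points between two high survival proportions usually needs several hundred patients per arm, so 456 for the whole trial looked too small. This is the only justification of sample size in the protocol, and it concerns the primary endpoint. If the stated power is wrong by a wide margin, a non-significant result would be judged against an 80% chance of detection that the trial never had, and the ethics committee would have approved the trial on a figure that its own assumptions do not support.

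**Working it through.** **Inputs, all from the protocol.** Survival at 1.5 years: p1 = 0.86, p2 = 0.92 (Section 8). Two-sided alpha 0.05, z = 1.960 (Sections 8 and 9). Power 0.80, z = 0.842 (Section 8). Dropout 10% (Section 8). Allocation 1:1 (Section 5.1). Total enrolled 456 (Section 8).

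**Step 1: try to reproduce 456.**

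Two proportions, unpooled variance, per arm:

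n = (1.960 + 0.842)² × (0.86 × 0.14 + 0.92 × 0.08) / 0.06² = 7.849 × 0.194 / 0.0036 ≈ 423

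That is 846 in total, and 846 / 0.9 ≈ 940 enrolled.

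Log-rank, Schoenfeld, assuming proportional hazards. The hazard ratio is ln 0.92 / ln 0.86 = 0.553, and its logarithm is −0.593. Deaths needed:

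D = 4 × 7.849 / 0.593² ≈ 89.4

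The mean probability of death by 1.5 years is (0.14 + 0.08) / 2 = 0.11. So N = 89.4 / 0.11 ≈ 813 evaluable, or 406 per arm, and about 903 enrolled.

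The other standard formulas agree:

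| Formula | Evaluable per arm | Total enrolled (÷ 0.9) |
|---|---|---|
| Schoenfeld (89.4 deaths) | 406 | 903 |
| Arcsine | 419 | 932 |
| Unpooled proportions | 423 | 940 |
| Pooled proportions | 426 | 946 |
| Freedman (94.7 deaths) | 430 | 956 |
| Continuity-corrected | 458 | 1,019 |

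None comes near 456 in total. Rounding deaths or patients up at each step raises these totals slightly (Schoenfeld to 909, Freedman to 960).

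**Step 2: power at the stated total.** 456 × 0.9 = 410.4 evaluable, or 205.2 per arm. Expected deaths by 1.5 years: 410.4 × 0.11 ≈ 45.

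- Two proportions, pooled variance under the null: z = (0.06 × √205.2 − 1.960 × √(2 × 0.89 × 0.11)) / √0.194 = −0.018, so power is 49%.
- Schoenfeld: z = √45.1 × 0.593 / 2 − 1.960 = 0.031, so power is 51%.
- Freedman gives 49%. A simulated log-rank test (5,000 runs) also gives 49%.
- With no dropout at all (228 per arm), the three formulas give 53 to 56%.

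**Step 3: what 456 in total could detect.** Keeping 86% in controls and 410 evaluable, 80% power is reached at intervention survival of 94.2% (two proportions) or 93.9% (log-rank). The corresponding hazard ratios are about 0.39 and 0.42, against 0.553 implied by Section 8.

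**Step 4: read 456 as per arm.** The total would be 912, with about 821 evaluable and 821 × 0.11 ≈ 90 deaths. Power is 80.4% (Schoenfeld), 78.5% (two proportions) or 78.1% (Freedman), which is close to the claim. From the other direction, Schoenfeld needs 90 deaths (rounded up), and 90 / 0.11 / 0.9 / 2 ≈ 455 enrolled per arm.

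**Step 5: would a one-sided test explain it?** Section 9 rules it out. One-sided 0.05 would still need about 711 (Schoenfeld) to 817 (continuity-corrected) enrolled, and 410 evaluable would give only 61 to 64% power.

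**The case against.** The strongest objection is that the 50% figure counts deaths only up to 1.5 years. The primary endpoint has no stated horizon, and Section 8 uses 1.5-year survival as an input without saying that the analysis stops there. With longer follow-up there are more deaths: under a constant hazard ratio of 0.553, about 410 evaluable patients reach 80% log-rank power after roughly 3.2 to 3.4 years of fixed follow-up. This stands as a condition on the result. It does not rescue the stated figure, because the protocol gives no accrual or follow-up period of that length and frames the calculation at 1.5 years. The intervention also ends at 1 year (Section 5.1), so a constant effect to year 3 would be a strong assumption. Three years of fixed follow-up gives about 455 in total only before dropout, and about 505 after it.

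A second objection is that the per-arm explanation is not proven. That is right. Of the standard formulas, only Schoenfeld comes within a few patients of 456 per arm after dropout (451, or 455 with rounding up); the others give 466 to 510. A one-sample formula against a fixed 86%, doubled and without dropout, gives 458, although it is not valid for a randomised comparison. The origin of the figure is therefore an inference, but the mismatch does not depend on it.

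Leaving the formula to a statistical analysis plan would be acceptable. It does not help here, because the protocol states the number, the power and every input, and these disagree.

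**Conclusion.** The concern holds. On the protocol's own inputs, 456 patients in total give about 50% power for 86% versus 92% survival judged at 1.5 years. The stated 80% needs about twice as many patients: 903 to 1,019 enrolled across the standard formulas, and 89 to 95 deaths by the log-rank formulas instead of about 45. If the assumed benefit is real, the trial is about as likely to miss it as to find it.

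The result assumes 1:1 allocation, two-sided 0.05, 10% dropout treated as loss of evaluable patients, and, for the log-rank figures, proportional hazards with deaths counted to 1.5 years. Dropping the dropout allowance raises power only to 53 to 56%. That 456 is a per-arm number is the likeliest explanation, but it remains an inference.

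**What to change.** Correct Section 8 so that the number, the power and the assumptions agree, and say whether 456 is a total or a per-arm figure. Naming the formula would let a reader check it.

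- **If 456 is the total:** state that about 410 evaluable patients give about 50% power for 86% versus 92% at 1.5 years, and 80% power only if survival in the intervention arm is about 94%. This is a change of wording and needs no extra patients; its price is a less favourable power statement. If the sponsor relies on longer follow-up for more deaths, the period and the assumed hazard ratio over it must be written down.
- **If 456 was meant per arm:** write 456 per group, 912 in total, with 78 to 80% power depending on the formula. This doubles enrolment.

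Either correction amends the protocol, so Section 10 calls for renewed ethics approval. The first is enough to make the document correct.
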